1.1 Study objectives and endpoints

The purpose of Part 1 of the study was to evaluate the safety, tolerability, pharmacokinetics (PK), pharmacodynamics (PD) and efficacy; and to estimate the Maximum Tolerated Dose (MTD) of branaplam.

The purpose of Part 2 of the study is to characterize dose-exposure-response to inform dose selection of orally administered branaplam in subjects with Type 1 SMA.

The purpose of Part 3 of the study is to provide continuous treatment with branaplam to patients who have participated in Part 1 or 2 of the study and have completed at least 52 weeks of treatment. In addition, Part 3 provides long-term safety and efficacy follow-up for patients treated with branaplam for more than 52 weeks.

1.1.1 Primary objective(s)

[figure not shown]
Objective	Endpoint
Part 1: Determine the safety and tolerability of ascending weekly doses and estimate the MTD of branaplam in infants with Type 1 SMA.	For all parts: 
Physical examVital signsECG and echocardiographic evaluationSafety laboratory parametersOphthalmologic examinationNeurologic examinationNerve conduction study: sensory nerve action potential (SNAP), nerve conduction velocity (NCV) for sensory and motor nerves and ulnar nerve compound motor action potential (CMAP)Adverse events
Part 2: Evaluate the safety and tolerability of 2 doses of branaplam administered for 52 weeks in subjects with Type 1 SMA.	
Part 3: Assess long-term safety and tolerability of extended oral/enteral, once a week branaplam treatment in patients with type 1 SMA who have had at least 52 weeks of treatment in either Part 1 or 2 study of this protocol.	

1.1.2 Secondary objective(s)

Objective	Endpoint
Part 1, Part 2, Part 3:	Part 1, Part 2, Part 3:

To evaluate branaplam pharmacokinetics in plasma after single and repeated doses of branaplamTo evaluate the effect of branaplam on growth parametersTo evaluate the effect of branaplam on respiratory function	
AUC and Cmax of branaplamGrowth measurements (body weight, head circumference, length and chest circumference)Pulse oximetry*, respiratory rate, paradoxical breathing assessment, chest circumference during quiet breathing*.

To evaluate the effect of branaplam on infant motor development.	
CHOP-INTEND infant motor scale up to the age of 36 months.Hammersmith Infant Neurologic Examination
In addition to the above for Part 2:	In addition to the above for Part 2:

• To evaluate the efficacy of branaplam on motor and developmental milestones	
• Preservation of oral feeding

• To evaluate the efficacy of branaplam on the ability to sit without support.	
• Ability to sit without support over time as assessed by HINE-2
In addition to the above for Part 3:	In addition to the above for Part 3:

• To evaluate the efficacy of branaplam on motor and developmental milestones	
• Preservation of oral feeding

• To evaluate the efficacy of branaplam on the ability to sit without support.	
• Ability to sit without support, stand or walk over time as assessed by HINE-2

• To assess the proportion of infants who are alive and are without permanent ventilation over time	
• Adverse Events and deaths over time

• To assess the impact of treatment with branaplam on time-to-event (death, permanent ventilation)	
• Adverse Events and deaths over time

Note: * these secondary endpoints will not be analysed in this analysis (see Section 4 for a rationale)

2 Statistical methods

2.1 Data analysis general information

A statistical vendor (CRO), [REDACTED] to which the statistical analysis is outsourced, will perform all planned analyses, i.e. IAs (Section 2.13) as well as the final analysis after the final database lock. Details of the analyses for Parts 1, 2, and 3 at the upcoming final database lock are outlined in this document.

Data will be analyzed using SAS® version 9.4 (or higher).

Descriptive summary statistics, unless otherwise specified, for continuous variables include number of non-missing observations (n), mean, median, standard deviation (SD), Q1 (25th percentile), Q3 (75th percentile), minimum and maximum, while for categorical variables frequencies and relative percentages will be reported.

Descriptive analyses will be stratified by part as follows:

- For disposition, demographics, baseline characteristics, and medical history, and protocol deviations, by parts (Part 1, Part 2, Part 1 & 2, Part 3)
- For all other summaries and figures: Part 1 & 3, Part 2 & 3, and Total (where applicable)

For analysis summaries, Part 1 will not be stratified by titration dose, while Part 2 will be stratified by the two treatment doses. For patients in Part 3 from Part 2, the fixed dose in Part 2 will be used as a strata; thus transitions from a low dose to a higher dose in Part 3 will not be analysed separately.

Individual graphs, such as spaghetti plots by study part and treatment and panel plots by study part and subject (with actual dose displayed as background shading) relative to time from first dose (in months) will be provided for selected endpoints, as applicable. Individual graphs relative to calendar age (in months) such as growth curve plots of vital signs, etc. will also be presented.

Listings will be provided by study part, cohort and subject.

The following treatment labels will be used for all tables, listings and figures in the order provided here:

- **Part 1:**
LMI070 0.3125 mg/kg, LMI070 0.625 mg/kg, LMI070 1.25 mg/kg, LMI070 2.5 mg/kg,
LMI070 3.125 mg/kg
- **Part 2:**
LMI070 0.625 mg/kg, LMI070 2.5 mg/kg
- **Part 3 (from Part 1):**
LMI070 0.625 mg/kg, LMI070 2.5 mg/kg, LMI070 3.125 mg/kg
- **Part 3 (from Part 2):**
LMI070 0.625 mg/kg, LMI070 2.5 mg/kg

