In this study, **'last contact with the subject'** will be the end of study visit, unless an SAE occurs. However, to ensure subject safety, every SAE must be reported to Novartis:

- occurring until 30 days after the last study visit, regardless of causality
- occurring after the 30 days period, if a causal relationship to study treatment is suspected

'Nominal visits' Nominal visits are defined as all scheduled visits as per the clinical study protocol including the EOS visits. The definition of nominal visit excludes unscheduled visits.

'Safety cutoff' Unless explicitly otherwise stated (e.g. SAEs and deaths), data up to and including the safety cutoff will be included in the analysis and data beyond this time point for a given subject will be excluded from the safety analysis. The safety cutoff is defined as the minimum of

- the study day the patient leaves study Parts 1, 2*, or 3
- the database cutoff date (the Final Database Lock date)
- 30 days after permanent study drug discontinuation.
- day of first dose of alternate treatment for SMA

'Efficacy cutoff' Unless explicitly otherwise stated, data up to and including the efficacy cutoff will be included in the analysis and data beyond this time point for a given subject will be excluded from the efficacy analysis. The efficacy cutoff is defined as the minimum of

- the study day the patient leaves study Parts 1, 2*, or 3
- the database cutoff date (the Final Database Lock date)
- day of first dose of alternate treatment for SMA

The following rules will be applied to assign data to part 3:

- a. For datasets/endpoints that have planned visit numbers populated (e.g. HINE, CHOP-INTEND, etc.), the visit number included in the IFC dataset under 'Consent for

additional follow-up study phase' which is the first visit of Part 3 (as confirmed by Cmed) will be used:

i.e. assessments with visit numbers that are \geq that IFC visit number will be assigned to Part 3.

b. For datasets/endpoints that do not have planned visit numbers populated (e.g. AEs, Feeding status, etc.), the visit date that corresponds to the above IFC visit number will be used:

i.e. assessment dates that are \geq that IFC visit date will be assigned to Part 3. In particular, AEs or concomitant medication with start date time \geq that IFC visit date will be assigned to Part 3.

In general, data collected at a visit during the Part 3 will be analysed together with the part the subject came from (i.e. 'Parts 1 & 3', 'Parts 2 & 3').

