2.5 Analysis of the primary objective

The primary objective of Part 1 was analyzed in the Interim 3 CSR. This analysis will not be repeated here. Details of the planned analysis can be found in Appendices 5.4.

The primary objective of Part 2 is to evaluate the safety and tolerability of multiple doses of branaplam for 52 weeks in subjects with Type 1 SMA. The primary objective for Part 3 is to assess long-term safety and tolerability of extended oral/enteral, once a week branaplam treatment in patients with type 1 SMA who have had at least 52 weeks of treatment in either Part 1 or 2 study of this protocol. The analyses are described below in the safety section. All information obtained on adverse events will be displayed by initial and administered dose and subject.

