2.8 Safety Analyses

In general, data assigned to Part 3 (section 2.1.1) will be analysed together with the part the subject came from (i.e. 'Parts 1 & 3', 'Parts 2 & 3').

Safety analyses will be conducted using the safety set (SAF). In Parts 1 & 3, subjects will be analyzed overall, with some graphical methods including the current dose; in Parts 2 & 3, the analyses will be summarized by actual treatment group. Unless explicitly stated otherwise, only data up to the safety cutoff (as defined in [Section 2.1.1](#)) will be included in the analysis and data beyond this time point for a given subject will be excluded from the safety analysis.

The assessment of safety will be primarily based on the frequency of adverse events (including death and non-fatal serious adverse events), and adverse events of special interest. Additional safety assessments include laboratory tests, ECG evaluations, echocardiograms, vital signs, ophthalmology, physical and neurophysiological examinations. Clinically significant findings

in these additional safety assessments will be reported as adverse events and analyzed as such. In addition, all safety assessments will be summarized or listed as appropriate.

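### The final analysis pools Part 2 with all Part 3 follow-up in its crude safety event tables, so none is limited to the 52-week period of Part 2 or to Part 3, the time frames of the two primary objectives

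*SAP*

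**What the plan says.** SAP 1.1.1 gives Part 2 and Part 3 different time frames. For Part 2: "Evaluate the safety and tolerability of 2 doses of branaplam administered for 52 weeks in subjects with Type 1 SMA". For Part 3: "Assess long-term safety and tolerability of extended oral/enteral, once a week branaplam treatment in patients with type 1 SMA", restricted to patients who have already had at least 52 weeks of treatment. SAP 2.5 restates the first ("The primary objective of Part 2 is to evaluate the safety and tolerability of multiple doses of branaplam for 52 weeks") and says that the analyses for both are those of the safety section.

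SAP 2.1 then fixes the columns. One group of tables is split by single part: "For disposition, demographics, baseline characteristics, and medical history, and protocol deviations, by parts (Part 1, Part 2, Part 1 & 2, Part 3". Everything else follows the pooled rule: "For all other summaries and figures: Part 1 & 3, Part 2 & 3, and Total (where applicable". SAP 2.1.1 repeats the pooling ("In general, data collected at a visit during the Part 3 will be analysed together with the part the subject came from"), and 2.8 repeats it for safety: "data assigned to Part 3 (section 2.1.1) will be analysed together with the part the subject came from".

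The SAP also derives a Part 3 flag. Under 2.1.1 and 2.8.2, an AE that starts on or after the date of the first Part 3 visit is assigned to Part 3. No crude event table is said to use that flag to show the two periods separately.

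**The concern.** Each objective asks what happened in a defined period. A crude percentage of patients who ever had an event, counted from first dose to the end of Part 3, describes neither period and rises as follow-up lengthens.

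Two features of the design add to this. First, the Part 2 cohorts opened one after the other (protocol section 3), so pooled follow-up can differ between the two doses, whereas the first 52 weeks are common to both. Second, protocol 3.5.3 reports that, after the 52-week analysis, sites were prompted to move patients to 2.5 mg/kg. SAP 2.1 keeps the fixed Part 2 dose as the stratum and does not analyse transitions separately, so events after a switch would count under 0.625 mg/kg. SAP 2.1.1 instead groups safety data by the dose with most exposure in each part, giving a dose combination that depends on what happened after Week 52. Neither rule, applied to pooled follow-up, gives the two-dose, 52-week description that the Part 2 objective calls for.

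**Working it through.** **1. The plan's own safety figure.** SAP section 3 says that no events in 6 patients rules out a true incidence above 50% with 95% confidence. Check: 0.5^6 = 0.0156, below 0.05. The one-sided 95% upper bound is 1 − 0.05^(1/6) = 39.3%. The statement is correct and conservative. It survives pooling, because no event over longer follow-up also means none by 52 weeks. A non-zero pooled count, however, does not show how many events fell within 52 weeks.

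**2. Which outputs can be read for which period.**

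| Output | SAP section | Period as written |
|---|---|---|
| Crude TEAEs (all, serious, drug-related, leading to discontinuation, most common) | 2.8.2 | Pooled |
| Laboratory shifts; newly occurring liver abnormalities | 2.8.4 | All post-baseline values, pooled |
| Vital-sign shifts | 2.8.6 | Post-baseline values, pooled |
| Echocardiography abnormality | 2.8.5 | Any time after baseline, pooled |
| QT/QTc threshold counts | 2.8.5 | Per assessment |
| Exposure-adjusted AEs and SAEs | 2.8.2 | By part, not defined |
| AESIs | 2.8.2.1 | By study part, not defined |
| Deaths | 2.8.3 | By study part, not defined |
| Kaplan-Meier: death, permanent ventilation or tracheostomy | 2.7.2 | Indexed by time; readable at 52 weeks |
| Completion, discontinuation and reasons | 2.1, 2.3.1 | Single parts |

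The first four rows are the gap. For the three undefined rows, the rule in 2.1 makes pooled columns the more likely meaning. On the other hand, time at risk in 2.4.1 ends at the end of the study part, which would also fit single parts.

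**3. Illustration of the effect on a crude percentage.** The documents do not fix the length of Part 3, so 2 to 4 years of total follow-up are assumed, with a constant hazard and 52 weeks taken as one year. If the 52-week incidence is p, the pooled incidence after t years is 1 − (1 − p)^t.

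| 52-week incidence | 2 years in total | 4 years in total |
|---|---|---|
| 10% | 1 − 0.9² = 19% | 1 − 0.9⁴ = 34% |
| 20% | 1 − 0.8² = 36% | 1 − 0.8⁴ = 59% |
| 30% | 1 − 0.7² = 51% | 1 − 0.7⁴ = 76% |
| 50% | 1 − 0.5² = 75% | 1 − 0.5⁴ = 94% |

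**4. Whether exposure adjustment repairs it.** Let r be the Part 3 event rate divided by the Part 2 rate, and y the further years in Part 3, equal for all patients. The pooled rate divided by the Part 2 rate is (1 + r·y)/(1 + y).

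- r = 1: the ratio is 1 for any y, so the pooled rate is right.
- r = 0.5: 1.5/2 = 0.75 at y = 1; 2.5/4 = 0.625 at y = 3.
- r = 2: 3/2 = 1.5 at y = 1; 7/4 = 1.75 at y = 3.

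A pooled exposure-adjusted rate therefore recovers the Part 2 rate only when the rate does not change after Part 2.

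**The case against.** The strongest case on the other side has four parts.

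First, a 52-week Part 2 analysis exists. Protocol 11.7 planned an internal analysis once all Part 2 patients had completed 52 weeks, protocol 3.5.3 reports its result, with comparable safety profiles, and SAP 2.13 mentions a fourth interim analysis of Parts 1 and 2. This is true and reduces the practical loss. But SAP 2.5 defers only Part 1 to an earlier report (the Interim 3 CSR). For Part 2 it points to the safety section of this SAP, and no interim of Parts 1 and 2 can answer the Part 3 objective.

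Second, exposure-adjusted incidence is planned and is the usual answer to unequal follow-up. Under a constant hazard it fully answers the point, so the percentages in step 3 show what happens to the crude tables only. It does not answer the point if rates change between Part 2 and Part 3, as step 4 shows.

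Third, a reader might infer that every event table is pooled and that nothing planned bears on either objective. The documents do not support that. Disposition is by single part, the Kaplan-Meier table can be read at 52 weeks, QT/QTc counts are per assessment, and by-visit summaries keep Part 2 weeks and Part 3 months apart through the visit windows. Exposure-adjusted AE, AESI and death tables may or may not be pooled.

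Fourth, the stakes are limited. All parts are declared non-confirmatory, Part 2 has 25 patients, and all AEs are listed, with listings by study part, cohort and subject. That stands, but listings are not a summary of the primary objective.

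**Conclusion.** The point holds for the crude TEAE, serious TEAE, laboratory and vital-sign shift, newly occurring liver-abnormality and any-time echocardiography tables. Their pooling is a stated rule, not missing detail, and it leaves both primary objectives without a crude event summary over their own period. For exposure-adjusted AEs, AESIs and deaths, the point is only that the part term is undefined.

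The size cannot be fixed from the documents. The range in step 3 rests on an assumed constant hazard and assumed total follow-up of 2 to 4 years. A reader might take it as a standing factor by which the pooled figure exceeds the 52-week one; it is not, because the ratio depends on the incidence and on follow-up. The pooling can be removed at little cost before the final tables are produced.

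**What to change.** In SAP 2.1 and 2.8, add two sets of event tables split on the existing Part 3 flag:

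- **Part 2 set:** from first dose to the day before the first Part 3 visit, or to the safety cutoff for patients who do not enter Part 3. Group by the Part 2 component of the dose grouping.
- **Part 3 set:** from the first Part 3 visit onward.

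Give each set its own time at risk. The formula in 2.4.1 starts at first dose, so the Part 3 version needs a start at the first Part 3 visit. With these limits no event falls between the two sets. Cutting the Part 2 set at Week 52 instead would lose events between Week 52 and Part 3 entry. The Part 2 window may run somewhat past 52 weeks for some patients, and its time at risk will show by how much.

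Keep the pooled tables as long-term summaries. State in 2.4.1, 2.8.2, 2.8.2.1 and 2.8.3 whether by part and by study part mean single or pooled parts. Reconcile the dose grouping in 2.1 (fixed Part 2 dose) with that in 2.1.1 (combination by exposure).

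The cost is additional tables from data and flags already planned; no new data collection is needed.

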2.1.1 General definitions

‘**Actual dose**’ will be derived as the current dose for each subject on a daily basis across the entire study; in the case of the day of a dose change, the new dose will be used.

‘**Treatment group**’ in Parts 2 & 3 will refer to the treatment group combination (as mentioned above) for efficacy analyses, and to the actual treatment for safety analyses (see definition below). In Parts 1 & 3, this will be Overall.

‘**Cohort**’ will refer to the initial dose for baseline or demographic characteristics.

The term ‘**Study Day**’ in this document relates to the Analysis Relative Day, Relative Start Day or Relative End Day as applicable. ‘**Study Day**’ is defined relative to the analysis reference date, which is the date of treatment assignment; it is the number of days from the reference date to the analysis date. For all dates on or after the analysis reference date, the study day is the difference to the analysis reference date plus one day (i.e. for date \geq reference date, study day = date - reference date + 1); for any dates prior to the analysis reference date, the study day is

simply the difference to the reference date (i.e. for date < reference date, study day = date - reference date). Thus, the Subject Reference Start Date is designated as Study Day 1, while the date directly prior to the reference date is defined as Study Day -1 (there is no Study Day 0).

'Baseline' is the last non-missing assessment obtained prior to the first administration of study drug. That means that if the measurement at the baseline visit is missing, then the previous measurement preceding baseline will be used as the baseline measurement. For pulse and blood pressure vital sign values, the baseline is the last non-missing value taken prior to the first administration of study drug.

'Treatment phase' includes the time interval on treatment and post-treatment follow-up. Any measurements taken after baseline will be considered as post-baseline measurements.

'Actual treatment' is defined as the treatment group the patient has most exposure to in each Part (for Parts 2 & 3), leading to a treatment group combination; in the case of two treatments having identical exposure, the higher dose will be used. This will be used for safety analyses.

'Calendar age' is defined as the age at the date of evaluation.

In this study, **'last contact with the subject'** will be the end of study visit, unless an SAE occurs. However, to ensure subject safety, every SAE must be reported to Novartis:

- occurring until 30 days after the last study visit, regardless of causality
- occurring after the 30 days period, if a causal relationship to study treatment is suspected

'Nominal visits' Nominal visits are defined as all scheduled visits as per the clinical study protocol including the EOS visits. The definition of nominal visit excludes unscheduled visits.

'Safety cutoff' Unless explicitly otherwise stated (e.g. SAEs and deaths), data up to and including the safety cutoff will be included in the analysis and data beyond this time point for a given subject will be excluded from the safety analysis. The safety cutoff is defined as the minimum of

- the study day the patient leaves study Parts 1, 2*, or 3
- the database cutoff date (the Final Database Lock date)
- 30 days after permanent study drug discontinuation.
- day of first dose of alternate treatment for SMA

'Efficacy cutoff' Unless explicitly otherwise stated, data up to and including the efficacy cutoff will be included in the analysis and data beyond this time point for a given subject will be excluded from the efficacy analysis. The efficacy cutoff is defined as the minimum of

- the study day the patient leaves study Parts 1, 2*, or 3
- the database cutoff date (the Final Database Lock date)
- day of first dose of alternate treatment for SMA

The following rules will be applied to assign data to part 3:

- a. For datasets/endpoints that have planned visit numbers populated (e.g. HINE, CHOP-INTEND, etc.), the visit number included in the IFC dataset under 'Consent for

additional follow-up study phase' which is the first visit of Part 3 (as confirmed by Cmed) will be used:

i.e. assessments with visit numbers that are \geq that IFC visit number will be assigned to Part 3.

b. For datasets/endpoints that do not have planned visit numbers populated (e.g. AEs, Feeding status, etc.), the visit date that corresponds to the above IFC visit number will be used:

i.e. assessment dates that are \geq that IFC visit date will be assigned to Part 3. In particular, AEs or concomitant medication with start date time \geq that IFC visit date will be assigned to Part 3.

In general, data collected at a visit during the Part 3 will be analysed together with the part the subject came from (i.e. 'Parts 1 & 3', 'Parts 2 & 3').

The safety cutoff applies to safety analyses only. The only exception to this are serious adverse events and deaths. Any SAEs occurring after the 30 days period, where a causal relationship to study treatment is suspected, will be reported. All deaths will be reported irrespective of safety cutoff.

In general, treatment emergent AEs are defined as events starting after the first dose of study drug that were absent pre-treatment, or events present prior to the first dose but increased in severity after the first dose. This assumes the same AE with increased severity is properly entered as a separate record in the database with start date being the date when severity increases and that a second AE with same severity won't be entered before the same AE is resolved.

For any other safety analyses based on post-baseline abnormalities compared to baseline (i.e. ECGs, vital signs, etc.), where either of the results is not available, the '**missing**' category will be included to avoid any abnormalities being overlooked.

When showing values over time, for subjects who prematurely discontinued the study, study completion visit assessments will be displayed as if they had occurred at the next scheduled visit.

The eGFR is calculated using the MDRD formula. $eGFR [mL/min/1.73 m^2] = 175 \times (\text{serum Creatinine [umol/L]/88.4}) - 1.154 \times (\text{age [years]}) - 0.203 \times (0.742 \text{ if female}) \times (1.212 \text{ if African American})$ ([Levey et al. 2007](#)).

